6.3 Site Pooling

Refer to Section [5.1.1.1.5](#).

6.4 Missing/Incomplete Date Conventions

Dates may be imputed with year, month, and day values under certain scenarios:

Table 6-4 Imputation Scenarios

Scenario	Complete			Imputable
	Year	Month	Day	
1	Yes	Yes	Yes	Complete
2	Yes	Yes	—	Yes
3	Yes	—	Yes	No ¹
4	Yes	—	—	Yes
5	—	Yes	Yes	No ¹
6	—	Yes	—	No ¹
7	—	—	Yes	No ¹
8	—	—	—	Yes

¹ Not allowed per database design.

Dates will be imputed initially toward a specified target date for imputable scenarios 2, 4, and 8, and adjusted against the latest reasonable dates. The initial imputed date is determined by the following algorithm:

Table 6-5 Initial Imputed Date Algorithm

Available Year (YYYY)	Available Month (MM)			
	Missing	< Target Month	= Target Month	> Target Month
Missing	Target Date	—		
< Target Year	YYYY-12-31	YYYY-MM-LD		
= Target Year	Target Date	YYYY-MM-LD	Target Date	YYYY-MM-01
> Target Year	YYYY-01-01	YYYY-MM-01		

YYYY = available start date year; MM = available start date month; LD = last day of the month.

6.4.1 Missing/Incomplete AE Start Date

AE start dates will be imputed as the minimum of the following:

- Initial imputed date, where target date = Treatment start date
- Complete end date

6.4.2 Missing/Incomplete Medication Start Date

Medication start dates will be imputed as the minimum of the following:

- Initial imputed date, where target date = Treatment start date – 1
- Complete end date

6.4.3 Missing/Incomplete AE/Medication End Date

AE and medication end dates will be imputed as the minimum of the following:

- Initial imputed date, where target date = Treatment end date + 30
- Death date

6.5 Efficacy Endpoint Conventions

No worsening of lobular inflammation or hepatocellular ballooning grade (2005) is defined as change from baseline ≤ 0 , where change from baseline = follow-up value minus baseline value.

6.6 Safety Endpoint Conventions

6.6.1 Adverse Events

6.6.1.1 Missing Intensity or Relationship

If the investigator is unable to provide the actual values, the following imputations will be applied for tabular summaries (listings will present data as missing):

Table 6-6 Missing AE Intensity and Relationship Imputation Algorithms

Missing Value	Imputation	Timing
Intensity	Mild	Pretreatment Period
	Severe	Treatment Period
Relationship	—	Pretreatment Period
	Related	Treatment Period

6.6.1.2 Possible Distant Spread of Toxin (PDSOT)

Not applicable.

6.6.1.3 AE Group of Interest

Elevations in biochemistry that are associated with liver injury have been identified as potentially important risks and are considered AESI for the study drug in this protocol. Biochemical criteria for suspected DILI are defined in protocol Section 11.3.6.4. Cases of suspected DILI as defined by the prespecified criteria in protocol Section 11.3.6.4 should be reported to the sponsor within 24 hours on the AESI form and will be adjudicated by a hepatologist with expertise in DILI and reviewed by the DSMB.

6.6.1.4 Major Adverse Cardiovascular Events (MACE)

MACE (major adverse cardiovascular events) will be evaluated based on pre-defined diagnostic criteria in accordance with current cardiovascular guidelines for MACE³⁻⁵ which consists of 4 endpoints, or MACE-plus:

1. cardiovascular death,
2. non-fatal myocardial infarction,
3. non-fatal stroke, and
4. hospitalization for cardiovascular causes (including unstable angina).

Cases of suspected MACE will be identified by carrying out surveillance for potential MACE that may become cases of confirmed CV events during the study by (1) reviewing reports of all Serious Adverse Events (SAEs), and (2) searching the database of Treatment-Emergent Adverse Events (TEAEs) for Standardized MedDRA Query (SMQ) terms for the following preferred terms: myocardial infarction, other ischemic heart disease, heart failure, ischemic central nervous system vascular conditions, hemorrhagic central nervous system vascular conditions. The preferred terms could include derivatives related to the above.

Those reports will be assigned to any of the 4-point MACE described as follows:

1. Cardiovascular Death

- Sudden cardiac death
- Fatal myocardial infarction
- Fatal stroke
- Other fatal cardiovascular events (e.g., death due to heart failure, arrhythmia, pulmonary embolism, aortic dissection/rupture, etc.).

2. Non-fatal Myocardial Infarction

- ST elevation myocardial infarction (STEMI)
- Non-ST elevation myocardial infarction (NSTEMI)

3. Non-fatal Stroke

- Ischemic/embolic
- Hemorrhagic
- Undetermined

4. Hospitalization for Cardiovascular Causes

- Acute coronary syndrome (ACS) or unstable angina requiring hospitalization (including urgent revascularization procedure)
- Heart failure requiring hospitalization

- Arrhythmia (non-fatal) not associated with ischemia events, i.e., treatment emergent atrial fibrillation, supraventricular tachycardia, ventricular tachycardia, high-grade AV-block or ventricular fibrillation

All preferred terms and cases will be identified prior to database lock.

The MedDRA SMQs are below:

Broad Term SMQ	Narrow Term SMQ
Cardiac arrhythmias (SMQ)	Arrhythmia related investigations, signs and symptoms (SMQ)
	Bradyarrhythmia terms, nonspecific (SMQ)
	Conduction defects (SMQ)
	Disorders of sinus node function (SMQ)
	Cardiac arrhythmia terms, nonspecific (SMQ)
	Supraventricular tachyarrhythmias (SMQ)
	Tachyarrhythmia terms, nonspecific (SMQ)
	Ventricular tachyarrhythmias (SMQ)
Cardiac failure (SMQ)	Cardiac failure (SMQ)
Central nervous system vascular disorders (SMQ)	Conditions associated with central nervous system haemorrhages and cerebrovascular accidents (SMQ)
	Haemorrhagic central nervous system vascular conditions (SMQ)
	Ischaemic central nervous system vascular conditions (SMQ)
	Central nervous system vascular disorders, not specified as haemorrhagic or ischaemic (SMQ)
Ischaemic heart disease (SMQ)	Myocardial infarction (SMQ)
	Other ischaemic heart disease (SMQ)

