Treatment-related TEAEs by severity	Overall summary and by SOC, PT, and severity 
 • Subjects categorized overall and within each SOC and PT for the most intense occurrence 
If more than one adverse event with the same preferred term was reported, then the adverse event with the greatest severity will be used.
	From treatment start date until 30 days after treatment end date or last follow up visit, whichever comes later	Categorical descriptive statistics
TESAEs	Overall summary and by SOC and PT	From treatment start date until 30 days after treatment end date or last follow up visit, whichever comes later	Categorical descriptive statistics

Parameter	Description	Timing	Methodology
Treatment-related TESAEs	Overall summary and by SOC and PT	From treatment start date until 30 days after treatment end date or last follow up visit, whichever comes later	Categorical descriptive statistics
TEAEs leading to study drug discontinuation	Overall summary and by PT	From treatment start date until 30 days after treatment end date or last follow up visit, whichever comes later	Categorical descriptive statistics
MACE and new onset of T2DM	Overall summary and by SOC and PT 
 Includes PTs, high level terms (HLTs), and/or standardized MedDRA queries (SMQs) defined in Section 6.6.1.3 	From treatment start date until 30 days after treatment end date or last follow up visit, whichever comes later	Categorical descriptive statistics
TEAEs by subgroups of age, sex, race, and ethnicity	Overall summary and by SOC and PT	From treatment start date until 30 days after treatment end date or last follow up visit, whichever comes later	Categorical descriptive statistics

SOCs will be sorted alphabetically; PTs will be sorted in descending frequency.

All AEs (including non-treatment-emergent events) recorded on the eCRF will be listed for individual subjects showing both verbatim and preferred terms.

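### The SAP's only MACE table row is defined by MedDRA search terms, not by the cases assigned to the four MACE components; the arrhythmia bullet and the two search lists also need reconciling

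*SAP*

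**What the plan says.** **Definition.** SAP 6.6.1.4 sets out a four-component MACE-plus: cardiovascular death, non-fatal infarction, non-fatal stroke, and "hospitalization for cardiovascular causes (including unstable angina". The fourth component has three bullets:

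- The first, for coronary events, is worded "Acute coronary syndrome (ACS) or unstable angina requiring hospitalization (including urgent revascularization procedure", so it states the condition of admission.
- The second also states it: "Heart failure requiring hospitalization".
- The third, for rhythm disorders, does not. It begins "Arrhythmia (non-fatal) not associated with ischemia events, i.e., treatment emergent atrial fibrillation, supraventricular tachycardia"; its list is completed by three other conditions (two ventricular arrhythmias and advanced conduction block).

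**Case finding.** The same section says "Cases of suspected MACE will be identified by carrying out surveillance for potential MACE that may become cases of confirmed CV events". The sources are all SAEs and a query search of the treatment-emergent events. The reports found are then assigned to the four components, and terms and cases are to be settled before database lock.

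**Search terms.** The running text names five topics: infarction, other ischemic heart disease, heart failure, and ischemic and hemorrhagic central nervous system conditions. The query table that closes the section also lists the full cardiac arrhythmia group, including "Arrhythmia related investigations, signs and symptoms (SMQ" and several queries labelled nonspecific.

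**Output.** Table 5-18 in SAP 5.1.1.4.2 has one row for MACE and new-onset type 2 diabetes, summarised overall and by system organ class and preferred term. Its content is described by term types ("Includes PTs, high level terms (HLTs), and/or standardized MedDRA queries (SMQs") and referred to Section 6.6.1.3. That section deals with liver-injury events of special interest and contains no MACE terms.

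**The concern.** MACE is a named safety endpoint in both parts (Protocol 12.4.1; SAP 4.2). The drug is to be taken for roughly 6 to 8 years (Protocol 9.3), and diabetes is common enough in this population to be a randomization stratum. The MACE count will therefore be read closely.

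Section 6.6.1.4 describes a sound two-stage process: search broadly, then classify. The specified table stops after the first stage. A row built from query terms would present suspected events as MACE, and its layout has no place for the four components. A preferred term does not show whether the subject was admitted or whether an infarction was fatal.

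The other two faults bear on the classification itself. If the hospitalization condition for arrhythmia is unclear, and the search for arrhythmia is unclear too, two people could follow the SAP and produce different lists of assigned cases. The section does not say who makes the assignment, so nothing else in it resolves the difference.

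**Working it through.** The documents state no MACE rate, expected count, margin or power, so there is no figure to reproduce. The check is a comparison of the SAP with itself, followed by an illustration of direction only.

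**Step 1. Follow three kinds of report through the SAP.**

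| Report | Found by the written five-topic list? | Found by the query table? | Meets a component of 6.6.1.4? | In the Table 5-18 row as written, if the query table supplies its terms? |
|---|---|---|---|---|
| Non-fatal infarction | Yes | Yes | Yes | Yes |
| Non-serious outpatient atrial fibrillation | No topic covers it | Yes | Unclear: heading says no, bullet wording allows it | Yes |
| Non-serious term found only by the arrhythmia signs-and-investigations query | No | Yes | No | Yes |

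The last two columns should agree. They disagree in the third line and cannot be compared in the second.

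**Step 2. The row's definition.** It rests on terms and queries, with no mention of assigned cases or components. Its cross-reference leads to the liver section. As written, it therefore has neither the right unit of counting nor a usable source for its terms.

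**Step 3. The arrhythmia bullet.** The component's heading is hospitalization, and the first two bullets repeat that condition. The third replaces it with treatment emergence. If the heading alone imposes the condition, the repetition in the first two bullets is redundant; if it does not, the third bullet admits outpatient events. The text supports either reading. The bullet is limited in two ways: it is a closed list of five rhythm disorders, and it excludes those associated with ischemia.

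**Step 4. The search lists.** Five topics without arrhythmia in the text, against the full arrhythmia group in the table. The text allows derivatives of its terms, but arrhythmia is not naturally a derivative of any of the five.

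**Step 5. Direction of the effect (all inputs assumed).** Let p be the true placebo MACE risk, RR the true ratio of CVC to placebo, and b the risk of extra hits, taken as equal in both arms. Then:

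- observed ratio = (p × RR + b) / (p + b)
- observed difference = (p × RR + b) − (p + b) = p × (RR − 1), which does not contain b

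With p from 1% to 3% and b from 1% to 10%:

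- RR 2.0, mildest case (p 3%, b 1%): (6 + 1)/(3 + 1) = 1.75
- RR 2.0, strongest case (p 1%, b 10%): (2 + 10)/(1 + 10) = 1.09
- RR 1.5, mildest case: (4.5 + 1)/(3 + 1) = 1.38
- RR 1.5, strongest case: (1.5 + 10)/(1 + 10) = 1.05

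If only assigned cases are counted and none is an extra hit, b = 0 and the ratio is undiluted.

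**The case against.** The case for leaving this alone has real substance.

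- **The definition is narrower than it may look.** A reader might infer that any treatment-emergent arrhythmia counts as MACE. It does not: the list is closed, ischemia-related arrhythmia is excluded, and the bullet stands under a hospitalization heading. The fault is ambiguity.
- **Outpatient atrial fibrillation is not certain to be captured.** If it is non-serious, it is found only if the query table prevails over the written list. The SAP does not say which prevails.
- **Non-specific signs do not meet the MACE definition.** Section 6.6.1.4 makes hits suspected cases only, and the change log in SAP Section 8 also describes the queries as a means of identifying cases. Such terms can enter only through the table row.
- **The row may simply be out of date.** It is shared with new-onset diabetes, uses generic wording, and cites a section near the right one. The change log records 6.6.1.4 and 6.6.1.5 as additions. Table specifications are in a separate document that is not available here and may be correct.
- **The harm is bounded.** Safety analyses are descriptive, with no prespecified hypothesis, so no powered test or decision rule is affected. Infarction and stroke terms remain visible by preferred term, and deaths are counted elsewhere in Table 5-18. Equal extra hits leave the absolute difference alone. Equality is itself an assumption: if the drug affected rhythm, these events could add to a signal.

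All of this stands and limits the claim. It does not remove the mismatch between the row and Section 6.6.1.4. An outdated row is still the row the SAP specifies, and in a descriptive analysis the displayed count is the evidence.

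**Conclusion.** The point holds in this form: as specified, the only MACE row tabulates search hits and cites the wrong section, although the SAP already plans to assign cases to four components. The arrhythmia bullet leaves the hospitalization condition unclear, and the written and tabulated search lists conflict.

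The likely effect is an inflated descriptive MACE count and, if extra hits are equal in the arms, a ratio closer to 1. The size is unknown. The range in the working (a true ratio of 2.0 appearing as 1.75 down to 1.09, or 1.5 as 1.38 down to 1.05) rests wholly on assumed risks and shows direction only. The difference between arms is unchanged under the same assumption, so it would be wrong to infer that every treatment difference is pulled towards zero. Nor do the documents support saying that outpatient arrhythmia is plainly included.

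The sponsor should correct this before database lock: it is a stated rule that gives the wrong count, and it is cheap to repair.

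**What to change.** 1. **Table 5-18.** Replace the MACE row with the number of subjects with at least one assigned MACE, overall and for each of the four components. Cite 6.6.1.4. Show query hits separately, labelled as candidates. Give new-onset diabetes its own row, citing 6.6.1.5.
2. **Arrhythmia bullet.** Align it with its heading by adding the hospitalization condition and keeping the five-type list. If outpatient events are intended, rename the component instead.
3. **Search lists.** Make the written list and the query table in 6.6.1.4 identical.

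A separate line combining cardiovascular death, infarction and stroke would be a reporting preference; the point does not depend on it.

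**Cost.** SAP wording and one revised table shell. Case identification before lock is already planned, so no new data are needed. The downside is fewer events in the headline MACE count, and so less precision for that summary.

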6.6.1.5 Type 2 Diabetes Mellitus (T2DM)

New-onset T2DM will be identified using the MedDRA preferred terms (PTs). TEAEs will be compared to the medical history to confirm new onset versus an existing condition.

The MedDRA PTs and PT codes are below:

Preferred Term	PT Code
Insulin-requiring type 2 diabetes mellitus	10053247
Type 2 diabetes mellitus	10067585

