### Key Assessments

During Part 1 of the study:

- A Screening visit is to occur within 3 months before the Baseline visit. The informed consent form for Study 3152-301-002 (Parts 1 and 2) and patient education materials about NASH, liver fibrosis, liver biopsy procedures, and study retention tools will be reviewed at the Screening visit.
- As part of Screening, assessment of serum laboratory tests (hematology and chemistry panels), serum hepatic fibrosis indices (non-invasive hepatic fibrosis index score combining standard biochemical values, platelets, ALT, AST, and age [FIB-4]; AST to platelet count ratio index [APRI]; and NAFLD fibrosis score [NFS]) and evaluation of liver stiffness via transient elastography (TE) or liver imaging (performed no more than 6 months prior to the first day of Screening at sites where available) will aid in identifying subjects with clinically significant liver fibrosis prior to proceeding with a new liver biopsy.
- A historical liver biopsy, obtained no more than 6 months prior to the first day of Screening, that meets protocol-required specifications, or a new liver biopsy will be evaluated by an independent central pathologist for all subjects as part of Screening to confirm histologic evidence of NASH and fibrosis Stages 2 or 3.
- Subjects meeting all other eligibility criteria and with suspicion of significant liver fibrosis (through clinical evaluation, hepatic fibrosis indices, and/or liver stiffness assessment [performed no more than 6 months prior to the first day of Screening]) will undergo a new liver biopsy during the Screening period. In randomized subjects, a second post-treatment liver biopsy will be collected at the Month 12 visit ( $\pm 2$  weeks).
- Fasting metabolic parameters, including lipid panel (triglycerides, total cholesterol, high-density lipoprotein [HDL], low-density lipoprotein [LDL], very low-density lipoprotein [VLDL]), glucose, insulin and hemoglobin A1c (HbA1c), will be measured at Baseline and at Months 3, 6, and 12.

- Samples for biomarkers of systemic inflammation, including interleukin (IL)-1 $\beta$ , IL-6, high-sensitivity C-reactive protein (hs-CRP), and fibrinogen will be collected at Baseline and at Months 3, 6, and 12.
- Samples of non-invasive serum hepatic fibrosis indices (FIB-4, APRI, NFS), ELF Score, and PRO-C3 will be collected at Months 6 and 12.

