### Key Assessments

During Part 2 of the study

- Screening will only be required for newly enrolled subjects and will not be required for subjects continuing their previously assigned blinded treatment from Part 1. A Screening visit is to occur within 3 months before the Baseline visit for any new subjects to be enrolled in Part 2. The informed consent and patient education materials about NASH, liver fibrosis, liver biopsy procedures, and study retention tools will be reviewed at the Screening visit for newly enrolled subjects.
- As part of Screening, assessment of serum laboratory tests (hematology and chemistry panels), serum hepatic fibrosis indices (including FIB-4, APRI, and NFS) and evaluation of liver stiffness via TE or liver imaging (performed no more than 6 months prior to the first day of Screening at sites where available) should be performed to aid in identifying subjects with clinically significant liver fibrosis prior to proceeding with a new liver biopsy.
- A historical liver biopsy, obtained no more than 6 months prior to the first day of Screening, that meets protocol-required specifications or a new liver biopsy will be evaluated for all subjects as part of Screening to confirm histologic evidence of NASH and fibrosis Stages 2 or 3.
- Subjects newly enrolled in Part 2 meeting all other eligibility criteria and with suspicion of significant liver fibrosis (through clinical evaluation, hepatic fibrosis indices, and/or liver stiffness assessment [performed no more than 6 months prior to the first day of Screening]) will undergo a new liver biopsy during the Screening period. Newly randomized subjects in Part 2 will undergo a further liver biopsy at Month 12 (within  $\pm 2$  weeks). A liver biopsy will be performed at the Month 60 visit ( $\pm 2$  weeks) for all subjects.
- Fasting metabolic parameters, including lipid panel (triglycerides, total cholesterol, HDL, LDL, VLDL), glucose, insulin, and HbA1c, will be measured at Baseline for newly randomized subjects and every 6 months through the end of study for all subjects.
- Samples for biomarkers of systemic inflammation, including IL-1 $\beta$ , IL-6, hs-CRP, and fibrinogen, will be collected at Baseline for newly randomized subjects and every 6 months through the end of the study for all subjects.

- Samples for non-invasive serum hepatic fibrosis indices (FIB-4, APRI, NFS), Liver Stiffness, ELF Score, and PRO-C3 every 12 months for all subjects

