## **12.4. Safety**

### **12.4.1. Safety Endpoints (Part 1 and Part 2)**

- Clinical adverse events, including major adverse cardiovascular events (MACE) and new-onset T2DM
- Clinical laboratory tests (hematology, chemistry, and fasting metabolic parameters)
- Physical examination
- Vital signs
- 12 lead ECG

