6.6.2 Clinical Laboratory Assessments

6.6.2.1 Potentially Clinically Significant Criteria

Any laboratory abnormalities deemed clinically significant by the investigator must be reported as an AE. A clinically significant abnormality is a confirmed abnormality (by repeat testing) that is changed sufficiently from Baseline so that in the judgment of the investigator a change in management is warranted. Any laboratory test showing abnormal results (including those recorded as AEs) that are believed to be possibly/probably related to study drug treatment will be repeated weekly (or as often as deemed prudent by the investigator) until the abnormality is resolved, returns to Baseline, or is otherwise explained. Laboratory assessments values meeting *any* of the following PCS low or PCS high criteria will be categorized as PCS:

Table 6-7 Clinical Laboratory PCS Criteria

Category	Parameter	SI Unit	PCS Criteria	
			PCS Low	PCS High
Chemistry	Albumin	g/L	< 0.9 × LLN	> 1.1 × ULN
	Alanine aminotransferase	U/L	—	≥ 3.0 × ULN
	Alkaline phosphatase	U/L	—	≥ 2.0 × ULN
	Aspartate aminotransferase	U/L	—	≥ 3.0 × ULN
	Bilirubin, total or direct	μmol/L	—	> 1.5 × ULN
	Calcium	mmol/L	< 0.9 × LLN	> 1.1 × ULN
	Chloride	mmol/L	< 0.9 × LLN	> 1.1 × ULN
	Cholesterol	mmol/L	—	> 1.3 × ULN
	Creatinine	μmol/L	—	> 1.3 × ULN
	Glucose, fasting	mmol/L	< 0.8 × LLN	> 1.2 × ULN
	Glucose, nonfasting	mmol/L	< 0.8 × LLN	> 1.4 × ULN
	Potassium	mmol/L	< 0.9 × LLN	> 1.1 × ULN
	Protein, total	g/L	< 0.9 × LLN	> 1.1 × ULN
	Sodium	mmol/L	< 0.9 × LLN	> 1.1 × ULN
	Triglycerides	mmol/L	—	> 2.0 × ULN
	Urea nitrogen	mmol/L	—	> 1.2 × ULN
Uric acid	μmol/L	—	> 1.2 × ULN	
Hematology	Basophils, absolute cell count	10 ⁹ /L	—	> 3.0 × ULN
	Neutrophils, absolute cell count	10 ⁹ /L	< 0.8 × LLN	> 1.5 × ULN
	Hematocrit	Ratio	< 0.9 × LLN	> 1.1 × ULN
	Hemoglobin	g/L	< 0.9 × LLN	> 1.1 × ULN
	Platelet count	10 ⁹ /L	≤ 0.5 × LLN	≥ 1.5 × ULN
	Red blood cell count	10 ¹² /L	< 0.9 × LLN	> 1.1 × ULN
	White blood cell count	10 ⁹ /L	≤ 0.7 × LLN	≥ 1.5 × ULN
Urinalysis	pH	—	< 0.9 × LLN	> 1.1 × ULN
	Specific gravity	—	—	> 1.1 × ULN

LLN = lower limit of normal value; ULN = upper limit of normal value; normal value provided by laboratory.

SI = Le Système International d'Unités (International System of Units).

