Fasting Metabolic Parameters	
The following parameters may be included, but are not limited to: Lipid panel: Cholesterol (total), High density lipoprotein (HDL), Low density lipoprotein (LDL), Triglycerides, Very low-density lipoprotein (VLDL), Glucose, Insulin, Hemoglobin A1c (HbA1c)
 
Part 1: Baseline, Months 3, 6, and 12 Part 2: Subjects continuing from Part 1: every 6 months through the end of the study Newly randomized subjects: Baseline, every 6 months through the end of the Study

Biomarkers	
The following parameters may be included, but are not limited to: Fibrinogen, High-sensitivity C-reactive protein (hs-CRP), Interleukin (IL)-1β, IL-6
 
Part 1: Baseline, Months 3, 6, and 12 Part 2: Subjects continuing from Part 1: every 6 months through the end of the study Newly randomized subjects: Baseline, every 6 months through the end of the Study

Category	Parameters
Other Tests: Part 1 and Part 2	
Screening only: Ferritin, Follicle-stimulating hormone, (FSH) for postmenopausal women only Hemoglobin A1c (HbA1c), Hepatitis B surface antigen (HBsAg), Hepatitis C virus antibody (HCVAb), HCV RNA (only if HCVAb positive), HIV-1 and -2 antibodies
 
Screening, Month 12 and annually thereafter: α-fetoprotein (AFP)
 
All visits Urine pregnancy test for females of childbearing potential only. Positive urine pregnancy tests will be confirmed with a serum test.

Hepatic Panel Testing	
Part 1 and Part 2: Baseline and Unscheduled Visits
 
The following parameters may be included, but are not limited to:
 
Baseline only Anti-liver cytosol type 1 (anti-LC1), Antinuclear antibody (ANA), Anti-liver/kidney microsome type 1 (anti-LKM1) antibodies, Anti-smooth muscle antibodies (anti-SMA), Immunoglobulin G (IgG), Hepatitis B core antibody (HBcAb), Hepatitis B surface antibody (HBsAb) titer
 
Unscheduled Visits Antimitochondrial antibodies (AMA), ANA, Anti-LKM-1 type antibodies, anti-LC1 antibodies, Hepatitis A virus immunoglobulin M (HAV-Ab IgM), Hepatitis B virus surface antigen (HBsAg), Hepatitis C virus antibody (HCVAb), Hepatitis D virus antibody, Hepatitis E virus RNA by PCR, Immunoglobulin G subclass 1, anti-SMA, Alkaline phosphatase (ALP), Alanine aminotransferase (ALT), Aspartate aminotransferase (AST), Direct bilirubin, Total bilirubin

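### New-onset T2DM is counted from two typed MedDRA terms over the whole Safety Population, which narrows the endpoint's own row and dilutes its absolute incidence

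*SAP*

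**What the plan says.** Protocol 12.4.1 lists among the safety endpoints for both parts: "Clinical adverse events, including major adverse cardiovascular events (MACE) and new-onset T2DM". The SAP repeats this in its objectives table (4.2) and in 5.1.1.4.

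The only operational rule is SAP 6.6.1.5: "New-onset T2DM will be identified using the MedDRA preferred terms (PTs". Its table holds two terms, type 2 diabetes mellitus and "Insulin-requiring type 2 diabetes mellitus". Whether a case is new is settled this way: "TEAEs will be compared to the medical history to confirm new onset versus an existing condition".

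The summary row is in SAP Table 5-18, shared with MACE and produced for the Safety Population. It says the row may draw on preferred terms, high level terms or SMQs, and cites Section 6.6.1.3 for them. Under SAP Table 5-2, percentages use the number of subjects in the population unless stated otherwise, and nothing is stated otherwise here.

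Glycaemic data are collected throughout. In Part 1, "glucose, insulin and hemoglobin A1c (HbA1c), will be measured at Baseline and at Months 3, 6, and 12" (Protocol 7.1.1, Key Assessments). In Part 2, "glucose, insulin, and HbA1c, will be measured at Baseline for newly randomized subjects and every 6 months through the end of study" (Protocol 7.1.2, Key Assessments). SAP Table 6-8 carries them as "Glucose, Insulin, Hemoglobin A1c (HbA1c". Neither document, as far as it can be read, uses these values to define new-onset T2DM.

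**The concern.** Two features of the rule act on the reported rate.

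The first is the numerator. An event recorded as diabetes without a type, or as raised glucose or HbA1c, codes to neither listed term and adds nothing to the row. A laboratory conversion reaches AE status only through investigator judgement: "Any laboratory abnormalities deemed clinically significant by the investigator must be reported as an AE". It must then also code to one of the two typed terms.

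The second is the denominator. Subjects with T2DM at entry cannot have a new onset. The medical-history check removes them from the numerator, but they stay in the percentage base.

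At stake is how far a low count can reassure. Treatment is estimated at 60 months (Protocol synopsis), in a disease that Protocol 5.1 ties to obesity and diabetes, so conversions are to be expected. MACE, in the same table row, is found by review of all SAEs plus several SMQs (SAP 6.6.1.4). No reason is given for treating the two so differently.

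**Working it through.** **Numerator: passages set side by side**

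1. SAP 6.6.1.5 names two preferred terms, both typed.
2. Table 5-18 seems to allow a wider set, but Section 6.6.1.3 contains only the text on liver-injury adverse events of special interest. The pointer is broken and does not widen the list. The MACE and T2DM terms are in 6.6.1.4 and 6.6.1.5.
3. No HbA1c, glucose or antidiabetic-drug criterion for this endpoint appears in either document.
4. Laboratory values go into change-from-baseline and toxicity-grade summaries (SAP Table 5-19). The list of potentially clinically significant criteria (Table 6-7) has limits for glucose but none for HbA1c. None of these counts conversions among subjects who were not diabetic at entry.

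Let s be the share of true new cases that reach one of the two terms. The documents give no value for s, so this part of the shortfall cannot be sized.

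**Denominator: arithmetic**

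The plan states no rate for this endpoint, so there is no figure to reproduce.

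Inputs, from Protocol 5.3.3 (Phase 2b study): documented T2DM in 58.6%, 52.8% and 40.3% of the three arms, randomized 2:1:1.

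Allocation-weighted prevalence:

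π = 0.50 × 58.6 + 0.25 × 52.8 + 0.25 × 40.3 = 29.3 + 13.2 + 10.1 = 52.6%

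If r is the incidence among subjects at risk, the incidence shown over the Safety Population is (1 − π) × r. The dilution factor is:

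1 / (1 − 0.526) = 1 / 0.474 = 2.1

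So of every 100 subjects in the denominator, about 53 could not have the event and about 47 could.

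Effect on the comparison, with the same π in both arms:

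- Risk difference shown = (1 − π) × (r_CVC − r_placebo), so it shrinks by the same 2.1.
- Risk ratio shown = (1 − π) r_CVC / [(1 − π) r_placebo] = r_CVC / r_placebo, so it is unchanged.

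Equal π is a fair approximation, because randomization is stratified by T2DM in Part 1 (Protocol 7.1.1) and for new subjects in Part 2 (SAP 4.1.1).

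For sensitivity to π, the lowest and highest arm values give 1 / (1 − 0.403) = 1.68 and 1 / (1 − 0.586) = 2.42.

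**The case against.** The strongest reply is that the endpoint is worded as a clinical adverse event. Protocol 12.4.1 lists laboratory tests, including fasting metabolic parameters, as a separate item. Finding an AE endpoint from coded AEs follows that wording, and adding a laboratory definition is partly a design preference. This stands. It is why the laboratory criterion belongs in a supportive definition and not in place of the AE count.

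A reader might infer that cases outside the two terms disappear from the report. The documents do not support that. All TEAEs are tabulated by system organ class and preferred term, so untyped diabetes and hyperglycaemia appear by arm. Laboratory shifts are summarised. Protocol 11.3.1.1.7 makes a confirmed abnormality that warrants a change in management an AE, and 11.3.1.2 asks for the diagnosis where it is known. Protocol 12.4.2.5 also plans a table of new concomitant medications. The loss is from one labelled row, and it is partial.

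A reader might also infer that the treatment comparison is distorted on every scale. With stratification by T2DM the ratio is nearly intact. Under blinding, under-capture by coding is plausibly similar in the two arms, though no data confirm this.

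Nor should 1.7 to 2.4 be read as uncertainty about prevalence. It is the spread across arms that Protocol 5.3.3 itself describes as unbalanced on T2DM, in a trial that also enrolled Stage 1 fibrosis.

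A careless laboratory definition would bring its own error. Strata rest on documented T2DM, and the HbA1c exclusion applies only above 9%, so undocumented diabetes at entry could be counted as new at the first on-treatment test. Repeat tests for confirmation are not guaranteed. Both points shape the fix.

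Finally, parts of the endpoint lists are blacked out and the SAP numbering skips 5.1.1.3.2, so other metabolic analyses may exist. Section 6.6.1.5 itself shows no sign of redaction.

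**Conclusion.** The point holds as a reporting weakness in a descriptive safety endpoint. As written, the new-onset T2DM row omits untyped diabetes and laboratory-only conversions, cites the wrong section for its terms, and uses a denominator that includes subjects who cannot have the event.

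The dilution of absolute incidence and risk difference is about 2.1-fold. That figure assumes baseline prevalence near the weighted Phase 2b value of about 53%, which this trial's population may not share. The risk ratio is largely unaffected. The further shortfall from coding is real in direction and unknown in size.

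No hypothesis is prespecified for safety endpoints (Protocol 12.4.2, SAP 5.1.1.4), so alpha, power and the primary conclusions are untouched. The documents report no diabetes signal for CVC; the issue is only that the plan does not fully measure an endpoint it names. It is worth correcting because the correction is cheap.

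**What to change.** Before database lock, amend the SAP as follows.

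1. In 6.6.1.5, widen the preferred-term list to include untyped diabetes terms.
2. In Table 5-18, replace the reference to 6.6.1.3 with 6.6.1.4 (MACE) and 6.6.1.5 (T2DM).
3. For this row, use as denominator the subjects in the Safety Population without documented T2DM at baseline.
4. Add a supportive definition with two routes: laboratory conversion, or a new antidiabetic drug started for diabetes. Laboratory conversion means HbA1c or fasting glucose at or above a threshold fixed before lock, on two post-baseline values (scheduled or repeat), in a subject whose baseline value was below that threshold. The baseline condition keeps undocumented diabetes at entry from counting as new onset by this route. Allowing two scheduled values removes the dependence on ad hoc repeats.
5. Report the AE-only count alongside, so that the effect of the wider definition can be seen.

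The cost is SAP wording and a little more programming on data already collected. Reported incidence will be higher. Some conversions seen on a single value will not be counted, for example a first high value at Month 12 with no later test in the database at the Part 1 lock.
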